6.2 Preparation/handling/storage/accountability

The investigator or designee must confirm appropriate temperature conditions have been maintained during transit for all study treatment received and any discrepancies are reported and resolved before use of the study treatment.

Only patients enrolled in the study may receive study treatment and only authorised site staff may supply or administer study treatment. All study treatments must be stored in a secure, environmentally controlled, and monitored (manual or automated) area in accordance with the labelled storage conditions with access limited to the investigator and authorised site staff.

A formal system for drug accountability will be implemented. The investigator, institution, or the head of the medical institution (where applicable) is responsible for study treatment accountability, reconciliation, and record maintenance (ie, receipt, reconciliation, and final disposition records).

6.3 Measures to minimise bias: randomisation and blinding

All patients will be centrally assigned to randomised study treatment using an IVRS/IWRS. Before the study is initiated, the telephone number and call-in directions for the IVRS and/or the log-in information and directions for the IWRS will be provided to each site.

Patients who meet the eligibility criteria will be randomised in a 1:1:1:1:1 ratio to high, intermediate or low dose of verinurad plus allopurinol, allopurinol or placebo.

Laboratory reports for sUA and UACR will be masked to guard against revealing group differences in treatment endpoints except during pre-screening and screening. The central laboratory will issue notifications to study sites if sUA or UACR values indicate potential health concerns.

If a patient withdraws from the study, then his/her enrolment/randomisation code cannot be reused. Withdrawn patients will not be replaced.

The IVRS/IWRS will provide to the investigator(s) or pharmacists the kit identification number to be allocated to the patient at the dispensing visit. Routines for this will be described in the IVRS/IWRS user manual that will be provided to each centre. For patients who need down titration, the investigator will need to use the IVRS/IWRS for allocation of new study drug kits for the lower dose.

The randomisation code should not be broken except in medical emergencies when the appropriate management of the patient requires knowledge of the treatment randomisation. The investigator documents and reports the action to AstraZeneca, without revealing the treatment given to patient to the AstraZeneca staff.

AstraZeneca retains the right to break the code for SAEs that are unexpected and are suspected to be causally related to an IP and that potentially require expedited reporting to regulatory authorities. Randomisation codes will not be broken for the planned analyses of data until all decisions on the evaluability of the data from each individual patient have been made and documented.

The IVRS/IWRS will be programmed with blind-breaking instructions. The blind may be broken if, in the opinion of the investigator, it is in the patient's best interest for the investigator to know the study treatment assignment. The sponsor must be notified before the blind is broken unless identification of the study treatment is required for a medical emergency in which the knowledge of the specific blinded study treatment will affect the immediate management of the patient's condition (eg, antidote available). In this case, the Sponsor must be notified within 24 h after breaking the blind. The date and reason that the blind was broken must be recorded in the source documentation and case report form (CRF) (electronic or paper), as applicable.

Study unblinding should not occur until database lock and all decisions on the evaluability of the data from each individual patient have been made and documented.

Individual treatment codes, indicating the treatment randomisation for each randomised patient, will be available to the personnel analysing the PK samples.

Provisions for interim analysis are described in Section 9.5.

6.4 Treatment compliance

Any change from the dosing schedule, dose interruptions, dose reductions, or dose discontinuations should be recorded in the eCRF.

The investigator is responsible for management of the IP from receipt by the study site until the destruction or return of all unused IP. The investigator(s) is responsible for ensuring that the patient has returned all unused IP. For the new dosing regimen, following Protocol Version 5.0 implementation, patients will be instructed thoroughly and receive new dosing card instructions at Visit 9. They will be instructed to take 1 tablet daily from one bottle of allopurinol/matching placebo and 1 capsule daily from each of two verinurad/matching placebo bottles that will be differentiated by the label colour.

Treatment compliance: The patient will be asked about compliance at each study visit starting from Visit 4 onwards. When study medication is returned, compliance will be assessed based upon patient's interview and a count of the tablets returned. Compliance should be between $\geq 80\%$ and $\leq 100\%$ of that prescribed. If the patient is not compliant with recording study drug doses during the study, then the period of non-compliance should be noted as a protocol deviation and the sponsor should be notified. Patients judged to be non-compliant may

continue in the study, but should be counselled on the importance of taking their study medication and applicable ancillary medications as prescribed. The investigator (or designee) will record the amounts of study medication dispensed and returned at each visit as described in Table 1 and Table 2, as well as document reasons for non-compliance in the source document. The dates of all study medication dosing, including interruptions, missed doses, or overdose, must be recorded on the eCRF. The administration of all study medications (including IPs) should be recorded in the appropriate sections of the eCRF.

6.5 Concomitant therapy

Any medication or vaccine including over-the-counter or prescription medicines, vitamins, and/or herbal supplements that the patient is receiving at the time of enrolment or receives during the study must be recorded along with:

- Reason for use
- Dates of administration including start and end dates
- Dosage information including dose and frequency

An increased risk of hypersensitivity has been reported when allopurinol is given with ampicillin, amoxicillin, ACE inhibitors, or diuretics, in particular thiazides, especially in renal impairment. It is recommended that in patients receiving allopurinol an alternative therapy is used where available.

Medication/class of drug:	Usage (including limits for duration permitted and special situations in which it is allowed):
Treatments known to lower albuminuria should be stable (consistent dosing for at least 4 weeks), eg, ACEi, ARBs, mineralocorticoid receptor antagonists, or sodium-glucose linked transporter-2 inhibitors.	Proteinuria-lowering therapies must not be started, and doses not changed, between screening and the end of the treatment period of the study unless required for patient safety. Patients on stable doses at study entry should continue on the same doses.
Any medication restricted by the allopurinol package insert; eg, vidarabine, uricosuric drugs such as probenicid and large doses of salicylate, chlorpropamide, warfarin, coumarin anticoagulants, phenytoin, theophylline, amoxicillin, ampicillin, cytostatics such cyclophosphamide, doxorubicin, bleomycin, procarbazine and alkyl halogenides, ciclosporin, didanosine, furosemide and other thiazide diuretics, ACEi, aluminium hydroxide.	Use in accordance with the allopurinol package insert. Case reports suggest concomitant ACEi therapy (eg, captopril and enalapril) enhance the risk of allopurinol- related hypersensitivity reactions. Hypersensitivity reactions can occur in the absence of ACEi therapy as in the presence of diuretics and renal dysfunction.

ACEi Angiotensin-converting enzyme inhibitor; ARBs Angiotensin receptor blockers

Table 10 Prohibited medications

Any other investigational drugs than provided in this study.

Any medication prohibited by the allopurinol package insert.

Mercaptopurine

Azathioprine

Any drug administered primarily to lower sUA, including XOIs such as febuxostat or topiroxostat, or URAT1 inhibitors such as lesinurad or benzbromarone.

Strong or moderate OATP inhibitors.^a

Examples: atazanavir, ritonavir, clarithromycin, cyclosporin, erythromycin, gemfibrozil, lopinavir, rifampin (single dose), simeprevir

CCI

OATP Organic anion transport polypeptide; URAT1 Uric acid transporter 1; XOI Xanthine oxidase inhibitor

^a Further information is available at:

https://www.fda.gov/Drugs/DevelopmentApprovalProcess/DevelopmentResources/DrugInteractionsLabelin g/ucm093664.htm#table5-2

6.5.2 Other concomitant treatment

Other medication other than that described above, which is considered necessary for the patient's safety and wellbeing, may be given at the discretion of the investigator and recorded in the appropriate sections of the CRF.

6.6 Dose modification

Study treatments will be titrated in discrete steps as shown in Table 8. Titration steps will be spaced at 4-week intervals to minimise the risk of skin reactions to allopurinol. Patients unable to tolerate the stepped dosage may be down-titrated only by reversing the assigned steps within treatment group, and verinurad and allopurinol dosages cannot be unpaired from the titration schedule. Patients who cannot tolerate the step-1 dose will be discontinued from IP and be followed for the remainder of the study.

When the new dosing regimen is introduced under Protocol Version 5.0, patients unable to tolerate the new dosing regimen will be down-titrated to the initial dosing regimen (ie, patients on 24 mg will be down-titrated to 3 mg, and patients in other cohorts will not be dispensed the matching placebo capsule). Additionally, patients who have been down-titrated and are receiving less than the randomized dose of verinurad/matching placebo at Visit 9 will not switch to the new dosing regimen introduced under Protocol Version 5.0.

In case patient down-titration was done in error, the patient can be up-titrated only after consultation with the medical monitor.

6.7 Treatment after the end of the study

After the end of the study patients can be treated with uric acid lowering therapy and/or other therapies for CKD or other conditions requiring treatment at the responsible physician's discretion.

7 DISCONTINUATION OF TREATMENT AND PATIENT WITHDRAWAL

7.1 Discontinuation of study treatment

Patients may be discontinued from IP in the following situations. Note that discontinuation from study treatment is NOT the same as a complete withdrawal from the study.

- Patient decision. The patient is at any time free to discontinue treatment, without prejudice to further treatment
- Adverse event
- Severe non-compliance with the Clinical Study Protocol
- Skin reactions and hypersensitivity
 - Study drug should be discontinued immediately at the first sign of a skin rash or other signs which may indicate an allergic reaction. Skin rash is a commonly-reported AE in patients taking allopurinol. Skin reactions may be severe and can be fatal.
 - Extra vigilance for the signs of hypersensitivity syndrome or Stevens-Johnson syndrome / toxic epidermal necrolysis is required and the patient should be informed of the need to stop treatment immediately and permanently at the first appearance of symptoms.
- Development of signs/symptoms of nephrolithiasis or potential renal injury
 - Guidelines for assessing possible renal injury or kidney stone and altering treatment are in Appendix F
- Development of AST or ALT ≥3xULN together with total bilirubin ≥2xULN as described in Section 8.3.8 and Appendix E
- If a patient becomes pregnant during the course of the study, the IP should be discontinued immediately and an AstraZeneca representative notified.

Patients who discontinue IP will be recommended to continue on the study and follow the original visit schedule without taking IP.

See the SoA for data to be collected at the time of treatment discontinuation and follow-up and for any further evaluations that need to be completed.

7.1.1 Temporary interruption of study treatment

Patients may temporarily interrupt IP administration, for instance based on criteria for Appendix F. Temporary interruption of IP does not mean discontinuation of follow-up or termination of study participation. Study assessments should continue. When the IP is resumed, last dose taken should be administered again. If temporary interruption of IP occurred during titration step, the patient should resume titration with the last tolerable dose given. In the event of an interruption exceeding 1 month the administration of IP can be re-titrated to avoid allopurinol induced hypersensitivity reactions, after communication with the sponsor or sponsor's representative.

7.1.2 Study termination

The sponsor designee reserves the right to close the study site or terminate the study at any time for any reason at the sole discretion of the sponsor.

The study may be stopped if, in the judgment of AstraZeneca, trial patients are placed at undue risk because of clinically significant findings that:

- Meet individual stopping criteria or are otherwise considered significant
- Are assessed as causally related to study drug
- Are not considered to be consistent with continuation of the study

Regardless of the reason for termination, all data available for the patient at the time of discontinuation of follow-up must be recorded in the CRF.

In terminating the study, the Sponsor will ensure that adequate consideration is given to the protection of the patients' interest.

7.1.3 **Procedures for early discontinuation of study treatment**

The investigator should instruct the patient to contact the site before or at the time if study treatment is stopped. A patient who decides to discontinue study treatment will always be asked about the reason(s) and the presence of any AEs. The date of last intake of study treatment should be documented in the CRF (electronic or paper). All study treatment should be returned by the patient at their next on-site study visit or unscheduled visit. Patients permanently discontinuing study treatment should be given locally available standard of care therapy, at the discretion of the investigator.

Patients who discontinue study treatment will attend the end of treatment visit as soon as possible after treatment discontinuation. Discontinuation of study treatment, for any reason, does not impact on the patient's participation in the study. The patient should continue attending subsequent study visits and data collection should continue according to the study protocol (including a follow-up visit, but no need to do another end of treatment visit). If the

patient does not agree to continue in-person study visits, a modified follow-up must be arranged to ensure the collection of endpoints and safety information. This could be a telephone contact with the patient, a contact with a relative or treating physician, or information from medical records. The approach taken should be recorded in the medical records. A patient who agrees to modified follow-up is not considered to have withdrawn consent or to have withdrawn from the study.

If a patient becomes pregnant during the course of the study, IP should be discontinued immediately and an AstraZeneca representative notified.

7.2 Lost to follow-up

A patient will be considered potentially lost to follow-up if he or she fails to return for scheduled visits and is unable to be contacted by the study site.

The following actions must be taken if a patient fails to return to the clinic for a required study visit:

- The site must attempt to contact the patient and reschedule the missed visit as soon as possible and counsel the patient on the importance of maintaining the assigned visit schedule.
- Before a patient is deemed lost to follow-up, the investigator or designee must make every effort to regain contact with the patient or next of kin by, eg, repeat telephone calls, certified letter to the patient's last known mailing address or local equivalent methods. These contact attempts should be documented in the patient's medical record.
- Efforts to reach the patient should continue until the end of the study. Should the patient be unreachable at the end of the study, the patient should be considered to be lost to follow-up with unknown vital status at end of study.

7.3 Withdrawal from the study

A patient may withdraw from the study (eg, withdraw consent), at any time (IP **and** assessments) at his/her own request, without prejudice to further treatment.

A patient who considers withdrawing from the study must be informed by the investigator about modified follow-up options (eg, telephone contact, a contact with a relative or treating physician, or information from medical records). Circumstances of withdrawal will be documented either in writing by patient (ICF re-signature) or investigator.

If the patient withdraws consent for disclosure of future information, the sponsor may retain and continue to use any data collected before such a withdrawal of consent.

If a patient withdraws from the study, he/she may request destruction of any samples taken, and the investigator must document this in the site study records.

A patient who withdraws consent will always be asked about the reason(s) and the presence of any AE. The investigator will follow up patients as medically indicated.

Patients who fail to meet the eligibility criteria must not, under any circumstances, be randomised or receive IP. There can be no exceptions to this rule.

Where a patient does not meet all the eligibility criteria but is randomised in error, or incorrectly started on treatment, the investigator should inform the AstraZeneca study physician or representative immediately, and a discussion should occur between the AstraZeneca study physician and the investigator regarding whether to continue or discontinue the subject from treatment. The AstraZeneca study physician or representative must ensure all decisions are appropriately documented.

In those cases where continuation of study therapy is judged not to present a concern related to safety and disease management, the rationale for continuing study therapy must be clearly documented. The patient should continue follow-up in accordance with defined study procedures.

See SoA, Table 1 for data to be collected at the time of study discontinuation and follow-up and for any further evaluations that need to be completed. All study treatment should be returned by the patient.

8 STUDY ASSESSMENTS AND PROCEDURES

Study procedures and their timing are summarised in the SoA.

The investigator ensures the accuracy, completeness, legibility, and timeliness of the data recorded and of the provision of answers to data queries according to the Clinical Study Agreement. The investigator will sign the completed eCRFs. A copy of the completed eCRFs will be archived at the study site.

Immediate safety concerns should be discussed with the sponsor upon occurrence or awareness to determine if the patient should continue or discontinue study treatment.

Adherence to the study design requirements, including those specified in the SoA, is essential and required for study conduct.

All screening evaluations must be completed and reviewed to confirm that potential patients meet all eligibility criteria. The investigator will maintain a screening log to record details of all patients screened and to confirm eligibility or record reasons for screening failure, as applicable.

The maximum amount of blood collected from each patient over the duration of the study, including any extra assessments that may be required, will not exceed 400 mL. Repeat or unscheduled samples may be taken for safety reasons or for technical issues with the samples.

8.1 Efficacy assessments

Laboratory efficacy assessments are shown in Table 11.

Table 11	Laboratory	efficacy	variables
----------	------------	----------	-----------

UACR	Clinical chemistry (serum or plasma)
U-Albumin (mg/dL) ^a	S-Uric Acid (mg/dL) ^b
U-Creatinine (g/dL) ^a	S-Creatinine (mg/dL) ^b
	S-Cystatin C (mg/L) ^b
	S/P-NT-proBNP

For derivation of UACR (primary outcome variable)

^b Secondary outcome variables

NT-proBNP N-terminal pro-brain natriuretic peptide

Urine samples will be gathered as 3 consecutive daily morning void samples of urine for each visit.

8.1.1 Primary outcome - UACR

The ratio of urinary albumin to urinary creatinine (milligrams of albumin per grams of creatinine) will be assessed by a central laboratory. The mean ratio will be reported for each time point based on all samples collected (FMV sample 1, 2, and 3).

First morning void urine samples will be used for assessment of UACR. Patients will receive a urine sample collection kit allowing them to collect the first morning void urine on 3 consecutive days. Collected samples will be refrigerated until they can be brought to the study site for further processing in accordance with the laboratory manual. Ideally the urine samples should be collected 2 days before, the day before and on the day of a study visit to minimise storage and transportation of collected samples.

If a patient has forgotten to collect one or more of the samples before a visit, then the samples should be collected on the up-to-3 consecutive days following the visit instead (with exception for the randomisation visit urine samples, which must be collected before treatment is started).

In the absence of results from 3 analysed samples, the UACR for a time point will be calculated based on the available results.

Urine samples collected for assessment of UACR CC must not be confused with urinalysis samples collected at study site during visits for assessment of safety parameters and pregnancy testing.

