For the new dosing regimen, following Protocol Version 5.0 implementation, patients will be instructed thoroughly and receive new dosing card instructions at Visit 9. They will be instructed to take 1 tablet daily from one bottle of allopurinol/matching placebo and 1 capsule daily from each of two verinurad/matching placebo bottles that will be differentiated by the label colour.

- ^b Only performed at Week 60 visit if this visit occurs before Protocol Version 5.0 implementation.
- c Vital signs include temperature, pulse rate, blood pressure measurement.
- ^d Serious adverse events will be collected from the time of signature of informed consent form at Visit 2, throughout the treatment period and including the follow-up period and last contact. Adverse events will be collected from the time of the first dose of IP. Changes in medical history between the time of signature of the informed consent form and the first dose of IP will be reported as medical history.
- For women of childbearing potential, pregnancy urine dipstick tests will be conducted on site. A serum pregnancy test will be done by central laboratory after 2 positive urine tests.
- ^f Mandatory HLA-B*5801 allele testing prior to randomisation for all patients. Patients known to be positive for HLA-B*5801 cannot be randomised.

g CC

- ^h Verinurad, allopurinol and oxypurinol (active metabolite of allopurinol) plasma concentrations will be assayed.
- ⁱ Study medication should be dispensed at end of visit
- ^j At Visit 5 (approximately 8 weeks after randomisation) through Visit 9, titration to step-3 target dose will only be allowed if the patient's eGFR was ≥30 mL/min/1.73m² at Visits 3 and 4.

Table 2Schedule of activities – Extension treatment, end of treatment, and follow-up period (Visits 11 through 14
applicable only to patients who passed Week 60 prior to Protocol Version 5.0 implementation)

Visit	For all patients: End of treatment (EOT)/early discontinuation ^a	For all patients: Follow up visit (4 weeks after EOT/early	Details in CSP section or				
	11	12	13	14		discontinuation/ last scheduled, numbered visit ^b)	Appendix
Week	72	84	96	108			
Window	±7d	±7d	±7d	±7d		±7d	
Full physical examination					X	Х	Section 8.2.2
Brief physical examination	Х			х			Section 8.2.2
Vital signs °	х	х	х	Х	x	х	Section 8.2.3
Weight	х	х	х	Х	x	х	Section 8.2.2
ECG					X	х	Section 8.2.4
Concomitant medication	Х	Х	Х	Х	X	х	Section 6.5
Adverse events ^d	Х	х	х	Х	X	Х	Section 8.3

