4.1.2.9 Week 47 (Visit 9)

At the time of implementation of Protocol Version 5.0, a new dosing regimen will be introduced to assess the higher dose of 24 mg verinurad. Patients in the 3 mg verinurad cohort

who will have Visit 9 planned after the amendment implementation in the respective country/site and who have signed ICF for the new dosing regimen will be switched to 24 mg dose at Visit 9. Patients who do not consent should be discontinued from the study at a subsequent visit.

To introduce the new 24 mg dose, a new dosing regimen will be initiated across treatment arms to maintain blinding. For verinurad dosing, all patients in the new dosing regimen will receive 2 capsules through addition of a matching placebo capsule, with the exception of those who switched from the 3 mg to 24 mg dose, where two 12-mg verinurad capsules will be given. Allopurinol dosing will remain the same.

Note: Patients will only be allowed to switch to the new dosing regimen's treatments introduced under Protocol Version 5.0 if the patient's eGFR was \geq 30 mL/min/1.73m² at Visit 8. Management of patients with eGFR <30 mL/min/1.73m² at Visit 9 should be discussed with the medical monitor.

- Place phone calls on the day before the visit to remind patients to record the time and date of the study medication intake on the day of the visit
- Collect first morning void samples from 3 days before visit
- Collect untaken study medication
- Update concomitant medication
- Record AEs
- Record vital signs
- Record weight
- Obtain blood samples for post-dose PK and sUA (drug taken at home, date and time of drug intake should be recorded)
- Obtain blood samples for efficacy assessments (s-UA, creatinine, eGFR, Cystatin C, NTproBNP)
- Perform pregnancy urine dipstick test for women of childbearing potential; after 2 positive urine tests, a serum pregnancy test is to be done by central laboratory
- Prior to Protocol Version 5.0, IVRS/IWRS and dispense titration Step-3 dose (Note: Titration to step-3 target dose will only be allowed if the patient's eGFR was ≥30 mL/min/1.73m² at Visits 3 and 4.)
- Dispense containers for morning voids

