4.1.2.12 End of treatment (occurs at 60 weeks for patients on new dosing regimen following Protocol Version 5.0 implementation)/early discontinuation

Following the implementation of Protocol Version 5.0, all patients will discontinue treatment at Visit 10. The following assessments will be conducted at the end of treatment/early discontinuation visit.

- Collect first morning void samples from 3 days before visit (for primary CCI biomarkers)
- Record AEs
- Update concomitant medication
- Perform full PE
- Record vital signs
- Record weight
- Obtain 12-lead ECG
- Obtain blood samples for clinical chemistry and haematology, efficacy assessments (s-UA, creatinine, eGFR, Cystatin C, NT-proBNP), PK, CCI
- Obtain urine for safety assessment (dipstick urinalysis)
- Study drug return and accountability

4.1.2.13 Follow up visit (4 weeks after end of treatment/early discontinuation/last scheduled, numbered visit)

- All patients (including any patients who have discontinued treatment with investigational product [IP]) should return for their Visit.
- Collect first morning void samples from 3 days before visit (for primary CCI biomarkers)
- Update concomitant medication
- Record AEs
- Perform full PE
- Record vital signs
- Record weight
- 1
- Obtain 12-lead ECG

- Obtain blood samples for clinical chemistry and haematology, efficacy assessments (s-UA, creatinine, eGFR, Cystatin C, NT-proBNP) CCI
- Obtain urine samples for safety assessment (dipstick urinalysis)
- Perform pregnancy urine dipstick test for women of childbearing potential; after 2 positive urine tests, a serum pregnancy test is to be done by central laboratory

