8.5 Pharmacokinetics

Whole blood samples will be collected for measurement of plasma concentrations of verinurad, allopurinol and oxypurinol (active metabolite of allopurinol) as specified in the SoA. Instructions for the collection and handling of biological samples will be provided by the sponsor or analytical test site. The actual date and time (24-hour clock time) of each sample and date and time (24-hour clock time) of previous dose taken will be recorded in the CRF (an electronic bottle cap or another method may be used to assist in capturing the information).

The PK blood samples will be taken at 5 different visits:

- (Visit 6) Week 12: pre-dose; ie, visit must take place in the morning and the patient must take the study medication at the clinic after pre-dose PK has been taken.
 - A subset of at least 95 patients (19 patients per arm, considering some patients may terminate the study before Visit 6) will have samples taken pre-dose followed by post-dose blood samples within 3 to 4, 4 to 5, 5 to 6, and 8 to 9 h windows (sample taken at each time window).
- (Visit 7) Week 20: study medication taken at home, PK blood sample during the visit.
- (Visit 8) Week 34: study medication taken at home, PK blood sample during the visit.
- (Visit 9) Week 47: study medication taken at home, PK blood sample during the visit.
- (Visit 10) Week 60: study medication taken at home, regardless of dosing regimen, PK blood sample will be collected post dose during the visit.

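### The late-collection rule for urine samples is not suspended when treatment stops at Week 60, so off-drug voids can enter the 12-month UACR

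*Supplement*

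**What the plan says.** **Collection and averaging (Protocol Section 8.1.1).** Each UACR time point uses first morning voids from three consecutive days, ideally ending on the visit day. Forgotten samples are to be made up late: "then the samples should be collected on the up-to-3 consecutive days following the visit instead". One visit is exempt, "with exception for the randomisation visit urine samples, which must be collected before treatment is started". On averaging, the section says "The mean ratio will be reported for each time point based on all samples collected (FMV sample 1, 2, and 3"). If fewer than three results exist, "the UACR for a time point will be calculated based on the available results". Nothing separates voids taken before a treatment change from those taken after it.

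**Treatment stop (Section 4.1.2.12).** "Following the implementation of Protocol Version 5.0, all patients will discontinue treatment at Visit 10". Patients whose Visit 10 came before implementation kept their current supply and stop at their next visit (Section 4.1.2.10).

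**Dosing around the visit.** Treatment is taken once daily in the morning (Section 6). For Week 60, Section 8.5 specifies "study medication taken at home, regardless of dosing regimen, PK blood sample will be collected post dose during the visit".

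**Visit 9 (Section 4.1.2.9).** Eligible 3 mg patients "who have signed ICF for the new dosing regimen will be switched to 24 mg dose at Visit 9". The visit-day dose is taken at home, and a footnote to Table 1 adds: "Study medication should be dispensed at end of visit".

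**Use of Week 60.** The footnote to Table 4 places Month 12 at 60 weeks of treatment. UACR at 12 months is a secondary endpoint (Section 9.4.1.2). The only 12-month comparison named in Section 9.4.2.2 is 24 mg versus placebo, both on the two-capsule regimen.

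**The concern.** The randomisation exception shows that the protocol recognises the principle: samples meant to describe one treatment state should not be collected in another. Version 5.0 made Visit 10 a planned treatment stop for patients reaching it after implementation, but the exception was not extended to it. A patient who forgets the Week 60 samples is therefore told to collect them when the drug is already being withdrawn, and the results are averaged as on-treatment values.

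At stake is the 12-month UACR comparison of 24 mg with placebo. Placebo patients have no drug effect to lose. If the effect wanes after stopping, late voids move only the active arm, and they move it towards placebo. The comparison rests on a subset of the 3 mg arm (Section 2.3), so on fewer than the 145 patients per arm in the sample size calculation, and no power is stated for it.

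**Working it through.** **1. The plan's own figure.** The plan gives no number for late sampling. Its power statement concerns Week 34 and is not in dispute. With 145 per arm, log difference 0.29, SD 1.0 and two-sided alpha 0.1:

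power = Φ(0.29 / √(2/145) − 1.645) = Φ(2.469 − 1.645) = Φ(0.824) = 79.5%, against 80% stated.

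**2. Timing at Week 60.** Day 0 is the visit, with the last dose taken at home that morning. The table assumes that the first void precedes the usual time of the morning dose.

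| Void | Time since last dose | Daily doses missed | State |
|---|---|---|---|
| Day +1 | about 24 h | 0 | same interval as any on-treatment first void |
| Day +2 | about 48 h | 1 | off drug |
| Day +3 | about 72 h | 2 | off drug |

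If only the forgotten samples are replaced, starting on day +1:

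- one forgotten: no off-drug void;
- two forgotten: one of three voids is off drug;
- three forgotten: two of three are off drug.

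**3. Timing at Week 47, for patients who switch.** The new supply is handed out at the end of the visit, after that day's dose. The first 24 mg dose is therefore due on the morning of day +1, after the first void. Voids on days +2 and +3 follow one and two doses of 24 mg.

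**4. Scale, as an illustration only.** Let f be the share of patients with all three Week 60 voids late, and d1, d2, d3 the shares of the log effect lost on days +1 to +3. Treating the mean of the three ratios as close to their geometric mean:

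attenuation = f × L, with L = (d1 + d2 + d3)/3 and d1 = 0.

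- Without rebound, L is at most (0 + 1 + 1)/3 = 0.667. With an arithmetic mean and a true ratio of 0.75, the limit is 1 − ln[(0.75 + 1 + 1)/3]/ln(0.75) = 1 − 0.0870/0.2877 = 0.698.
- L = 0.5 requires d2 + d3 = 1.5, an average loss of 75% on days +2 and +3.
- Take a true 25% reduction (log effect 0.2877), borrowed from the design assumption for the high dose. With f = 5% and L = 0.25, the effect is 0.2877 × (1 − 0.0125) = 0.2841, measured as a 24.7% reduction. With f = 20% and L = 0.667, it is 0.2877 × (1 − 0.1333) = 0.2493, measured as 22.1%.

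Both f and L are assumptions. The Phase 2a study reported full effect at its first on-treatment assessment, at 1 week. That concerns onset and does not show how much is lost 48 to 72 hours after the last dose.

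**The case against.** **The rule does little harm.** The day +1 void is on treatment in every practical sense, and a patient replacing a single sample contributes nothing off drug. This stands, and it confines the problem to patients who forgot at least two samples. In addition, Table 1 drops the dispensing of new containers at Week 60 after implementation. That makes late collection less likely but does not prevent it, because containers are handed out at Visit 9.

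**The SAP may select samples by date.** No SAP is shown, and it could do so. But the protocol tells patients when to collect and says that all samples are averaged. Unless something overrides that, the off-drug voids are included.

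**Post-discontinuation data are included anyway.** Section 9.4.2.1 says this of the primary Week 34 analysis, for patients who stop early. At Week 60 the stop is planned for everyone still treated, and whether a void is off drug depends only on who forgot a sample.

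**Stronger readings that a reader might infer.**

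- *The primary endpoint is affected.* The rule sits under the primary outcome, but treatment continues after Visit 8, so late Week 34 voids are not off drug through this rule.
- *Visit 9 is spoiled as the reading before 24 mg.* Days +2 and +3 can follow 24 mg doses, but Week 47 is not an endpoint and no described analysis uses it as a reference.
- *The effect shrinks by 5% to 10%.* This follows from f = 10% to 20% with L = 0.5, but it multiplies two values that the documents do not supply.

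**Conclusion.** The point holds for Week 60. As written, Sections 8.1.1 and 4.1.2.12 together allow up to two of the three voids behind a patient's 12-month UACR to be taken after one and two missed doses, although Month 12 is defined as time on treatment. The direction is towards no effect in the secondary 24 mg versus placebo comparison, provided that the drug lowers UACR and its effect wanes on stopping.

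The size cannot be derived from the documents. The illustration suggests a modest loss unless late collection is common and offset is fast. The comparison is outside the confirmatory hierarchy (Section 9.4.4), and Section 9.4.2.2 allows it to be descriptive only. The Week 47 aspect is minor. The change is still worth making because it is cheap and applies a principle that the protocol already uses at randomisation.

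**What to change.** Extend the exception in Section 8.1.1 to the planned Week 60 end-of-treatment visit. Samples should be collected before treatment stops, if necessary by rescheduling within the existing ±7-day window, or at the latest on the morning after the last dose. Voids dated later should not be averaged into Week 60. The exception should target the planned stop, since early discontinuers are already off drug at their end-of-treatment visit. Repeat the rule in the laboratory manual, and have the SAP apply it using the date of each void.

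As a minor addition, apply the same date rule at Week 47, so that voids taken after the first dose of the new regimen are not averaged into that visit.

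**Cost.** One or two sentences and a date check. A few patients will have fewer than three Week 60 samples, which Section 8.1.1 already allows. Occasionally a patient who forgot all three, was not rescheduled and missed the next-morning void will have no Week 60 value, in an already small 24 mg group. Rescheduling to a later day also needs supply to cover the extra days, and the version history cites a shortage of investigational product. Accepting the next-morning void limits both costs.
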